## **Neurodevelopmental Follow-Up**

Each center site in this study has a Neonatal Follow-Up Clinic that performs neurodevelopment testing on infants from discharge up to three years of life by certified examiners as part of standard of care. Thus, developmental follow-up data will be available from all study subjects, regardless of intervention, and free of charge. As part of standard of care, each site will complete the Bayley Scales of Infant and Toddler Development® 3rd Edition, on preterm infants at 18 to 24 months' corrected age (CA). The primary subtests of interest include *Fine Motor* (prehension, motor speed and planning, perceptual-motor integration, reaching, grasping, and object manipulation), *Gross Motor* (dynamic movement [i.e., walking, jumping, running, stairs, etc.], motor planning, balance, and perceptual-motor integration), *Cognition* (puzzle assembly, object completion, means-ends manipulation, representational play, counting, and matching colors), and *Language* (receptive and expressive language). These data will be recorded,

analyzed, and correlated with feeding outcomes in the neo-and post-natal period, gene expression data, and intervention status. In addition, growth parameters including head circumference, length and weight will be recorded.

Feeding behavior plays a significant role in neurodevelopmental outcomes. Recent findings from the NICHD Neonatal Research Network (NRN) indicated at 18 months' CA, premature infants with a history of feeding difficulties are more likely to have language delay. Neuromotor status and days on mechanical ventilation are important risk factors associated with these outcomes. A follow-up of feeding status will be completed when our study infants reach 18 months' CA using the NICHD NRN 18-month Feeding-Growth-Nutrition Questionnaire. This questionnaire includes a simple checklist format about medical history since the NICU (re-hospitalization, primary cause, time period, LOS, time in ICU), medications, seizures, supplemental oxygen and respiratory monitoring, oromotor skills (independent feeds, dependent oral feeds, limited oral feeding, no oral feeding), NG or TPN feeds, feeding behaviors (aversion, swallowing-dysphagia), aspiration (food down windpipe, choking), spit-ups, high calorie supplements, oral diet texture (thin vs thickened liquids, soft solids, table food), and surgical operations. Completion time by the parent is 15 minutes or less. The feeding questionnaire and a pre-posted return envelope will be mailed to the parent when a given study infant attains 17.5 months of age. A cover letter will accompany the 3-page questionnaire explaining that a nurse/study specialist from this research project will be available to assist with the questionnaire.

Official Title: Somatosensory Modulation of Salivary Gene Expression and Oral Feeding in Preterm Infants

NCT number: NCT02696343

Document Date: 3-31-24

Statistical Analysis Plan.

Primary Outcome: Gene Expression

In this randomized controlled clinical trial, we analyzed salivary developmental gene expression changes in extreme and very preterm infants randomized to receive either therapy with the NTrainer feeding system or a 'Sham' mode (blind pacifier) to assess the effect of therapy on the developing infant. Salivary samples were collected at a series of timepoints, beginning with the initiation of therapy through the learning process of oral feeding or to transfer to an outlying hospital. The primary goal of this study was to assess and compare differences in gene expression patterns over time between groups. The expression of six genes involved in 1.) memory: *CDH13*; oral development: *FOXP2* and *WNT3*; 3.) sensory integration: *NPHP4*, and *PLXAN1*; and hunger signaling: *NPY2R*, along with two reference genes for proper normalization were measured via RT-qPCR for each subject at 6 timepoints. The raw CT values were normalized for each subject and timepoint by subtracting the geometric mean of the reference genes from the mean expression of each gene (deltaCT). These deltaCT values were used for the remainder of the analysis. A positive deltaCT value indicates that the target gene had lower expression than the reference gene; conversely increasing deltaCTs are indicative of decreasing expression. In order to determine changes in gene expression, one way and two-way ANOVA analysis in R [1] was used. Initially, the analysis was done to assess expression pattern changes over time for 1.) the cohort as a whole, 2.) based on treatment status, and 3.) by sex. Given that the timepoint measurements are done on the same subject, repeated measure ANOVA and subject for which all time points were not measured were excluded from the analysis. Subsequently, the analysis was extended by grouping subjects by bronchopulmonary dysplasia (BPD) status, looking at the effect over time, the effect of treatment status and the interaction of the two. BPD was defined based on NIH criteria.

Secondary Outcomes: Non-nutritive Suck Dynamics and Growth in Daily Oral Feeds

A-priori power calculation indicated that a sample size of 110 was required for 80% power, with an assumed correlation of 0.60 among repeated measures and a small effect over time (Cohen's $f = 0.10$). This effect was considerably smaller than those observed in our previous empirical data ($f = 0.22-0.24$), suggesting adequate power for the final sample of 114 neonates in this study.

Linear mixed modeling (LMM) analysis was performed for non-nutritive suck (NNS) variables including NNS Bursts/minute, NNS Suck Cycles/minute, NNS Amplitude, NNS Spatiotemporal Index, and the transition to independent oral feeds based on daily measures of percent oral intake (%PO) to examine the effects of GA, PMA, sex (male, female), respiratory diagnosis (non-BPD, BPD), treatment (NTrainer, Sham), intervention phase (0, baseline), (1, low-dose), (2, high-dose), (3, post intervention), and potential interactions. The models

accounted for nesting of repeated measurements within infants (i.e., intraclass correlation), and a proper error covariance structure was determined based on model fit (i.e., adjusted Akaike Information Criterion, Bayesian Information Criterion). In addition, locally estimated scatterplot smoothing (LOESS) analysis was conducted to estimate the trajectory of %PO growth over PMA. All statistical analyses were conducted using R [1] and SAS 9.4 [2].

References

1. R Core Team. R: A language and environment for statistical computing. R Foundation for Statistical Computing (2019) <http://www.R-project.org/>
2. SAS Institute. SAS/STAT 9.4 user's guide. (2002-2012).

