## Protocol

Preterm infants will be recruited at gestational age 240/7-286/7 weeks GA. Each infant will be randomized to receive either the PULSED NTrainer or SHAM intervention using a software random integer function in Minitab v.17 (www.minitab.com). As shown in Figure 1, infants assigned to the PULSED NTrainer group will receive a progressive dose of the pulsatile orocutaneous stimulation. Beginning at 30 weeks' PCA, these infants will receive 2 weeks of low-dose PULSED NTrainer stimulation (2 x 3-minute blocks) with a 1-minute stimulus 'off-period' between the stimulation blocks. This form of stimulation will be given simultaneous with tube feedings 3 times/day. The stimulus dose will then be increased over the next 2 weeks (3 x 3-minute blocks of PULSED NTrainer stimulation) with a 1-minute stimulus 'off-period' between the stimulation blocks, also given simultaneously with tube feedings 3 times/day. Preterm infants randomized to the SHAM condition will be given a regular silicone pacifier during tube feedings over the same time period.

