### **Saliva Collection, Processing, and Gene Expression Analysis**

*Saliva Collection:* Saliva samples will be collected from all enrolled infants on the first day prior to receiving either the SHAM or PULSED NTrainer intervention. This sample will serve as our baseline gene expression profile. Samples will then be obtained twice per week (~3 day intervals) up to the time of achievement of full oral feeds or discharge home from the hospital with either a nasogastric tube (NG) or gastrostomy tube.

Saliva samples at each site will be collected with techniques that have been optimized and validated through the [name] laboratory. Briefly, saliva samples will be collected with a 1 mL syringe, end caps removed and attached to low wall suction. Saliva will be collected for approximately 20 seconds and immediately stabilized in 500 µL of Qiagen's RNA Protect Saliva to halt gene expression changes, inhibit destructive RNases, and limit microbial overgrowth. Samples will be vortexed briefly and frozen at -20°C. Once frozen, samples are stable for up to 18 months prior to the need for total RNA extraction. Thus, samples from Nebraska and Santa Clara will be shipped once a month on ice overnight to the [name] laboratory at the Mother Infant Research Institute at Tufts Medical Center in Boston, MA for processing.

*Generation of a Saliva Biobank:* One additional saliva sample will be obtained each week from all enrolled subjects to generate a biobank repository. The rationale for this approach is twofold. First, it is possible that during shipment or processing, salivary RNA may be destroyed and not be of sufficient quality to incorporate into the study. Prior studies from this lab have demonstrated a 10% failure rate of gene amplification in saliva samples. Banking an additional sample each week from study subjects will ensure that we will limit loss of data points. Second, we anticipate that there are informative salivary biomarkers of oral feeding maturation that have yet to be identified. By generating a biobank of additional saliva samples that may be retrospectively interrogated on either a microarray gene expression platform or with RNASeq, we will have the potential to discover novel hypotheses about gene-gene interactions and/or transcriptional regulatory processes related to oral feeding in the preterm population.

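### The primary gene-expression ANOVA gives the pre-treatment saliva sample no stated role; this costs precision, not validity, by an amount that depends on effect shape and correlation

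*SAP*

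**What the plan says.** The SAP, under Primary Outcome: Gene Expression, sets the aim: "The primary goal of this study was to assess and compare differences in gene expression patterns over time between groups". The method is stated as "In order to determine changes in gene expression, one way and two-way ANOVA analysis in R [1] was used". It adds that repeated-measures ANOVA was used on deltaCT at six timepoints and that "subject for which all time points were not measured were excluded from the analysis". Analyses are listed for the whole cohort, by treatment status and by sex. An interaction is mentioned only in the later extension to BPD status.

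On the first sample, the SAP says: "Salivary samples were collected at a series of timepoints, beginning with the initiation of therapy". The protocol (Saliva Collection, Processing, and Gene Expression Analysis) takes saliva from every infant before the first NTrainer or sham session and says: "This sample will serve as our baseline gene expression profile". Sampling then continues until full oral feeding or discharge with a feeding tube.

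The SAP names no baseline covariate, change score or equal-baseline constraint for the primary outcome. Its secondary models are linear mixed models whose error covariance is chosen by AIC and BIC.

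**The concern.** Randomisation makes the expected arm difference at the pre-treatment sample zero. An arm-by-time ANOVA that includes this sample as an ordinary timepoint estimates that difference as if it were unknown. It then spends information on a quantity that the design already fixes. A model that uses the known zero answers the same question about pattern over time, with the same degrees of freedom for the arm comparison, and is more precise for most effect shapes.

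At stake is power for the primary outcome. Sample loss makes this matter more. Complete-case exclusion applies, and the protocol reports: "Prior studies from this lab have demonstrated a 10% failure rate of gene amplification in saliva samples".

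**Working it through.** **1. The plan's own sample size, and where its correlation belongs.** The only correlation in the documents is in the SAP's Secondary Outcomes section, "with an assumed correlation of 0.60 among repeated measures", with f = 0.10, 80% power and N = 110. Take a within-subject F test with noncentrality f² × N × m / (1 − r), alpha 0.05 (assumed) and two arms.
- m = 4 levels: 0.01 × 110 × 4 / 0.4 = 11.0, power 79.9%. N = 110 is reproduced.
- m = 6 levels: 0.01 × 110 × 6 / 0.4 = 16.5, power 89.7%; N = 87 would suffice.

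The calculation therefore fits the four intervention phases, not the six gene timepoints. For deltaCT, 0.60 is a borrowed value, so a range is needed.

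**2. Set-up.** Unit SD; n per arm; d = the five post-baseline arm differences; the baseline difference is zero; compound symmetry with correlation r. Both tests have 5 numerator df.
- Unadjusted arm-by-time noncentrality: (n/2)[d'd − (Σd)²/6]/(1 − r)
- Baseline constrained equal: (n/2)[d'd − r(Σd)²/(1 + 5r)]/(1 − r)

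The information lost is 1 minus their ratio. Under compound symmetry it is largest for a constant effect, where it equals 5(1 − r)/6, and zero when the effects sum to zero.

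**3. Numbers at n = 57 and r = 0.60.** This is an equal split of 114 with no exclusions; n/2 = 28.5 and r/(1 + 5r) = 0.15. The effect sizes are chosen here for illustration.
- Constant 0.30: d'd = 0.45, (Σd)² = 2.25. 28.5 × 0.075/0.4 = 5.34 against 28.5 × 0.1125/0.4 = 8.02.
- Ramp 0.1 to 0.5: d'd = 0.55, (Σd)² = 2.25. 28.5 × 0.175/0.4 = 12.47 against 28.5 × 0.2125/0.4 = 15.14.

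| Shape | Unadjusted | Adjusted | Loss | Power (F; 5 and 560 or 559 df) |
|---|---|---|---|---|
| Constant 0.30 | 5.34 | 8.02 | 33% | 38% vs 56% |
| Ramp to 0.50 | 12.47 | 15.14 | 18% | 78% vs 87% |
| Last two, 0.50 | 23.75 | 24.94 | 5% | 97.8% vs 98.4% |
| Last only, 0.50 | 14.84 | 15.14 | 2% | – |

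**4. Sensitivity to the correlation.** The AR(1) column compares the two tests with the covariance modelled correctly in both.

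| Shape | Compound symmetry, r = 0.3 to 0.7 | AR(1) 0.60 |
|---|---|---|
| Constant | 58% to 25% | 46% |
| Ramp | 38% to 13% | 51% |
| Last two | 12% to 3% | 19% |
| Last only | 5% to 1% | 11% |

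**5. Fewer infants.** If 10% of samples failed independently and none were rescued from the biobank, 0.9⁶ = 53% of infants would be complete: 57 × 0.531 ≈ 30 per arm. Simulated power under compound symmetry 0.60 (20,000 runs), Greenhouse-Geisser ANOVA against the adjusted joint test with unstructured covariance:
- 57 per arm: constant 37% vs 53%, ramp 78% vs 85%.
- 30 per arm: constant 19% vs 27%, ramp 44% vs 51%, last two 76% vs 75%, last only 52% vs 50%, sum-to-zero 55% vs 53%.

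The gain for a constant effect about halves, the ramp gain changes little, and late effects gain nothing. If compound symmetry fits and is used, the adjusted test at 30 per arm reaches 29% (constant), 54% (ramp) and 79% (last two).

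**6. Does the zero baseline difference survive complete-case selection?** It holds for all randomised infants. Sampling stops at full oral feeding, which therapy may affect, so completers may differ at baseline by arm. In a null simulation with assumed opposite-direction selection by arm, type I error of the baseline-covariate test rose from 0.05 to 0.09, and to 0.22 under strong selection. The unadjusted arm-by-time test stayed near 0.05. The selection strengths are assumptions; the documents give none.

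**The case against.** - **The ANOVA is a valid standard method.** Arm-by-time already contrasts later samples with the first. Simulated type I error was 0.047 at 57 per arm, under both compound symmetry and AR(1). This stands: a reader might infer that the primary comparison is biased or invalid, and nothing in the documents supports that.
- **The SAP does not name the between-arm test or say that the pre-treatment sample is the first of the six.** This stands as a condition. The stated aim and the start of sampling make both readings natural, but if only separate within-arm analyses are meant, the figures do not apply.
- **A single headline loss is unsafe.** This stands. A reader might take 33% as the ceiling and treat a late effect as unaffected. Both hold only near r = 0.60 under compound symmetry. At r = 0.3 a constant effect loses 58%; under AR(1) 0.60 a ramp loses more than a constant effect, and an effect in the last two samples loses 19%.
- **Some power comparisons change two things at once.** Under AR(1) 0.60 at 57 per arm, the sphericity-corrected ANOVA has 18% (constant) and 42% (ramp), and the adjusted unstructured test 45% and 53%. Part of that gap is the change of covariance model: with unstructured tests on both sides the pairs are 25% vs 45% and 27% vs 53%. The gap from the ANOVA should not be credited to baseline adjustment alone.
- **Adjusting in complete cases could do harm.** This stands and shapes the fix.
- **The 53% complete-case figure is pessimistic.** Agreed; the weekly banked sample exists to replace failed ones.
- **The SAP is written in the past tense.** This limits what can be changed, not whether the gap exists.

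**Conclusion.** The point holds as a moderate matter of efficiency. A designated baseline is collected in every infant, and the primary analysis gives it no stated role. The loss ranges from about 1% to 58% over the shapes and correlations examined; effects that sum to zero lose nothing under compound symmetry. The protocol says that treated infants "will receive a progressive dose of the pulsatile orocutaneous stimulation", so a growing effect is at least as plausible as a constant one. For the ramp, the loss is 38% to 13% under compound symmetry with r from 0.3 to 0.7, and 51% under AR(1) 0.60.

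This rests on the arm-by-time reading, the pre-treatment sample being first of six, illustrative effect sizes, and alpha 0.05 per gene. The documents support neither a claim of bias nor one fixed percentage for the loss.

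**What to change.** For each gene, fit a mixed model to deltaCT in all randomised infants who have a baseline sample, using every available timepoint rather than only infants with all six. Constrain the arm means to be equal at the pre-treatment sample and test the arm differences jointly over the five later samples (5 df). State that the pre-treatment sample is the first timepoint and which between-arm term is tested. Choose the covariance structure by the model-fit rule that the SAP already uses for its secondary models, before arm effects are viewed. Do not apply the equal-baseline constraint, or a baseline covariate, to the complete-case subset alone.

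The cost is SAP wording and model terms; no new data are needed. There are two downsides. The model relies on data being missing at random, which needs justification because sampling stops at full oral feeding. With an unstructured covariance and few infants, late or sum-to-zero effects may lose a few points of power against the sphericity-corrected ANOVA: one to three points under compound symmetry, and up to four under AR(1) 0.60 (29% vs 25% at 30 per arm). If results have already been seen, report this analysis beside the planned ANOVA and label it as added later.

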## Orocutaneous Stimulation Regimen

The NTrainer PULSED orocutaneous stimulus consists of a series of 6-cycle bursts which are delivered by a servo-controlled pneumatic amplifier (NTrainer System®) to the lumen of a standard silicone pacifier (e.g., WeeSoothe, or Soothe). These pneumatic bursts are frequency modulated (FM) from 2.8 to 1.6 Hz across the 6-cycle structure with a 2-second

pause period between bursts (Figure 2). Individual pressure cycles have a 31 millisecond (ms) rise/fall time to ensure a salient stimulus spectra with significant energy from DC-16 Hz. Frequency modulation is a physiologic feature of the non-nutritive suck (NNS) in preterm infants. A total of 34 bursts are presented in a 3-min block. A 1-minute rest period (no stimulation) occurs between stimulation blocks. Criteria for initiation of orocutaneous therapy include the following: 1) stable vital signs and not on continuous vasopressor medications; 2) tolerating enteral feeds in previous 48 hours; and 3) not intubated and mechanically ventilated. If the infant is on nasal intermittent positive pressure ventilation, continuous positive airway pressure or nasal cannula >2 liters per minute, then the FiO2 must be <40%.

[figure not shown]

Figure 2. Preterm infant receiving PULSED NTrainer stimulation during gavage feeding in the NICU. NG tube is placed through the left nares (not visible). Pneumatic stimulus control signals and output through the pacifier nipple are shown in the left panel. a) voltage-controller gate signal, b) intraluminal pressure (inside) the nipple, and c) mechanical displacement at the nipple cylinder wall.

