**Total RNA Extraction:** Salivary samples will be extracted for total RNA using established protocols optimized in the [name] laboratory. RNA extraction will occur with the QIAGEN RNeasy Protect Saliva Mini kit per manufacturer's instructions. On-column DNase treatment will be performed for each sample to eliminate genomic DNA contamination. Samples that are part of the biobank will be frozen at -80°C pending need for future analysis. Samples that will be used for RT-qPCR experiments will first undergo cDNA conversion with the Life Technologies SuperScript® Vilo™ kit per manufacturer's instructions. cDNA will be stored at -80°C in the Mother Infant Research Institute at Tufts Medical Center pending gene expression analysis.

**Gene Expression Analysis:** For the purpose of this study, we will interrogate each sample for nine genes, six target genes of interest and three reference genes for quality control and potential normalization of gene expression data. Genes to be analyzed in this study have been previously shown to be directly linked to oral feeding in the newborn and include *CDH13*, *FOXP2*, *NPHP4*, *NPY2R*, *PLXNA1*, and *WNT3*. The three reference genes include *GAPDH*, *HPRT1*, and *YWHAZ*, all of which have been shown to maintain stable gene expression across advancing PCA. All cDNA samples will undergo a targeted pre-amplification with a custom TaqMan® PreAmp Master Mix for all nine genes. This targeted approach to amplification will ensure that only those genes of interest will be amplified and not all genes across the transcriptome which may introduce bias. Pre-amplified cDNA will then undergo PCR with TaqMan® Fast Advance Master Mix on the Life Technologies Quant Studio™ 7 Flex Real-Time PCR System. This instrument is housed with the Mother Infant Research Institute at Tufts Medical Center and is an advanced state-of-the-art PCR machine and software system. All efforts will be made to adhere to the Minimum Information for Publication of Quantitative Real-Time PCR Experiments (MIQE) guidelines for this study. All samples will be run in duplicate with appropriate positive and negative controls.

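### The primary gene-expression analysis uses six undefined time points, complete cases only and no PMA or GA term, although the protocol provides dated twice-weekly samples that a mixed model could use

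*SAP*

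**What the plan says.** SAP, Primary Outcome: Gene Expression. The six target genes and the reference genes are measured by RT-qPCR "for each subject at 6 timepoints". The resulting deltaCT values go into one-way and two-way ANOVA, in repeated-measures form, by time, treatment and sex, and later by BPD status. Infants without all time points are left out. The section gives no definition, window or selection rule for the six, and names neither PMA nor GA as a model term.

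SAP, Secondary Outcomes. The suck and oral-intake measures are analysed with linear mixed models that include both GA and PMA and account for repeated measurements within infants.

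Protocol, Saliva Collection, Processing, and Gene Expression Analysis. A first sample is taken before any intervention: "This sample will serve as our baseline gene expression profile". After that, "Samples will then be obtained twice per week (~3 day intervals) up to the time of achievement of full oral feeds or discharge home". On assay, "we will interrogate each sample for nine genes". One further sample a week is banked, partly because about 10% of samples have failed to amplify in the past.

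Protocol, opening section. From 30 weeks' PCA, "these infants will receive 2 weeks of low-dose PULSED NTrainer stimulation", followed by two weeks at the higher level. The Orocutaneous Stimulation Regimen section makes the start conditional: "Criteria for initiation of orocutaneous therapy include the following", namely stability, feed tolerance and respiratory conditions. The PO Feeding Advancement section says that the study database logs the saliva sampling dates.

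**The concern.** The outcome is developmental gene expression in infants recruited from 24 0/7 to 28 6/7 weeks' GA, so age at sampling should be a main source of variation. The SAP replaces it with a six-level index that it does not define. If an infant starts late because the stability criteria are not yet met, or stops early because full feeds are reached, the same index refers to a different age. If the six points are spread over the period up to full feeds, the time axis depends on a post-randomisation outcome that the intervention is meant to change.

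The complete-case rule adds a second problem. An infant can lose all of their primary-outcome data through one failed assay or an early end of sampling. With the six points undefined, a reader also cannot tell which samples entered the primary test, or whether that choice was made before the data were seen.

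**Working it through.** **The plan's own figure.** The only power statement stands under the secondary outcomes: N = 110 for 80% power, f = 0.10, correlation 0.60. It gives neither the number of measures m nor alpha; I assume alpha = 0.05. With lambda = f² × N × m / (1 − rho), df1 = m − 1 and df2 = (N − k)(m − 1) for k groups:

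- m = 4: lambda = 0.01 × 110 × 4 / 0.40 = 11.0; power 0.799, and N for 80% power is 111. This reproduces the stated figure.
- m = 6: lambda = 0.01 × 110 × 6 / 0.40 = 16.5; power 0.897, and N for 80% power is 87 to 88. This does not reproduce it.

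So the statement fits four measures, which is also the number of intervention phases in the secondary models. The six-point primary analysis has no power statement of its own.

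**Scheduled samples.** Count = 1 baseline + 2 per week × weeks of sampling:

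- 2 weeks: 1 + 4 = 5
- 3 weeks: 1 + 6 = 7
- 4 weeks (full course): 1 + 8 = 9
- 6 weeks: 1 + 12 = 13

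None of these is six. An infant who stops at two weeks has five scheduled samples. If the time points are distinct scheduled samples, that infant cannot have six and is excluded.

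**What the six could be.** Two readings, neither stated in the documents:

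- Six consecutive samples. Five intervals of 3 to 3.5 days cover 15 to 17.5 days, so the series ends early in the third week of a 28-day course.
- Six points spread evenly to the end of sampling. For infants starting at 30 weeks, a three-week series puts the sixth point at 33 weeks and a six-week series puts it at 36. The same index then differs by three weeks of PMA.

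**Complete series at six points.** Inputs: 114 infants (SAP, Secondary Outcomes; the number in the gene analysis is not given) and 10% failure per sample (protocol). Assumptions: failures are independent, every infant has six planned samples, and nothing else is missing.

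- No biobank replacement: 0.9^6 = 0.531; 114 × 0.531 = about 61 infants.
- Every failure has an independent backup with the same failure rate: loss per sample 0.1 × 0.1 = 0.01; 0.99^6 = 0.941; 114 × 0.941 = about 107 infants.

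**Values used if exactly six samples per infant were assayed.** The total is 114 × 6 = 684.

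- No replacement: a mixed model uses 684 × 0.9 = about 616 values; complete cases use 60.6 × 6 = about 364.
- Full replacement: 684 × 0.99 = about 677, against 107.3 × 6 = about 644.

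**The case against.** Intervention is planned from 30 weeks' PCA, so the index partly tracks age. A repeated-measures ANOVA removes constant differences between infants. If expression changes about linearly and spacing is similar, a late start is such a difference and does little harm. Randomisation protects the comparison of arms against systematic GA imbalance at baseline. That the SAP treats time as categorical is inferred from the method it names. These points stand, and they limit the harm. They do not cover curved trajectories or unequal spacing, and the SAP gives no spacing.

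A reader might infer that assay results were discarded, and that at least a third of the data went unused. The documents do not support this. The SAP may mean that only six samples per infant were assayed, which would be an unexplained departure from the protocol and not a loss at analysis. Nor is nine a minimum: with seven scheduled samples, six leaves out one.

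A reader might also infer that using nine samples would by itself raise power. Under the SAP's complete-case rule it would leave fewer infants: 114 × 0.9^9 = about 44 without biobank replacement. Any gain depends on a model that accepts incomplete infants. The f and correlation used above are also not stated for gene expression.

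**Conclusion.** The point holds as a mismatch between schedule and analysis for which a better method is available. The six time points are undefined and not reconciled with the twice-weekly schedule. The complete-case rule can exclude infants for one missing sample. PMA and GA are absent from the primary model although the secondary models use both. The same index need not mean the same PMA.

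Under the stated assumptions, complete six-point series range from about 61 to about 107 of 114 infants. The true figure depends on how far banked samples replaced failures, which the SAP does not say, and on how many infants stopped sampling early. A mixed model keeps every infant with at least one valid sample.

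That the time axis depends on feeding outcome follows only if the six points are spread up to full feeds; the documents neither state nor exclude this. None of the plan's stated numbers is shown to be wrong. The change should be made, but the documents do not show that the primary result is invalid.

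**What to change.** - Make the primary analysis a linear mixed model for each gene, on every valid deltaCT from all randomised infants. Use actual PMA at sampling as time, with GA, arm and arm-by-PMA as terms and repeated measurements nested within infant, as already done for the secondary outcomes. State the functional form for PMA in advance, for example a spline.
- Define the six time points: which samples they are, the allowed windows, and whether banked samples could replace failures.
- Account for the other scheduled samples: collected, assayed, failed or not assayed.
- Report by arm how many infants the complete-case rule excludes and why. Keep the six-point ANOVA as a sensitivity analysis.

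If only six samples per infant were assayed, the same model with actual PMA still applies and needs no new assays.

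The cost is SAP wording and a re-analysis: the dates are in the database and the method is in use. The downside is that a functional form for PMA must be chosen. The SAP is written in the past tense, so a form chosen now should be labelled as set after the analysis. The mixed model also assumes that missing values are ignorable given the observed data and the model terms. Because sampling stops at full feeds, that assumption deserves a stated check.
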